# Aims for Phase I:

- 1. Develop a revised BIP manual for individual treatment delivery as a comparison treatment.
- 2. Develop a fidelity measure to distinguish F4C from BIP for therapist fidelity coding.
- 3. Establish acceptability and feasibility of F4C compared to traditional group BIP (BIP-G) and an individually delivered BIP (developed in aim 1 above; BIP-I). We will test the following specific research hypotheses:
  - i. Fathers randomized to F4C will have higher completion rates than those in either the BIP-I or BIP-G treatments.
  - ii. Fathers will report greater working alliance and satisfaction with F4C than either BIP condition
- 4. Assess initial intervention signal of F4C compared with BIP-I (developed in aim 1 above) and a group format BIP-G (current standard of care) program of comparable length. We will test the following specific research hypotheses:
  - i. Fathers receiving F4C will evidence greater improvement in reflective functioning (RF) and emotion regulation post-intervention compared to fathers receiving BIP-I or BIP-G.
  - ii. Fathers receiving F4C will show greater reductions in intimate partner violence (IPV) and child maltreatment (CM) over the 18 weeks of treatment compared to fathers receiving either BIP condition.
  - iii. Fathers receiving F4C will maintain reductions in IPV and CM in the 3 months following treatment.

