The RA will complete study assessments in person or via zoom with fathers, mothers and partners at baseline, immediately following intervention completion, at 6 and 12 month follow-ups. Each measure and timing of assessment are outlined in Table 1.

Table 1. Assessment	Rater	Baseline	Weekly During	Monthly During	Post- intervention	6& 12 Month- FU
Schedule			Intervention	Intervention		_
ir v Out comes						
Family Socialization Interview Revised (FSI-R)  – IPV module	Masked Coder	X			X	Х
Time-line follow-back for IPV (56, 57)	Father, Mother, Current Intimate Partner		Х			
Abusive Behavior Inventory (ABI)	Father, Mother, Current Intimate Partner	X			X	X
Court and Arrest Records	N/A	X				Х
Child Maltreatment and Parenting Outcomes						
Child Protective Services Records	N/A	X				X
Family Socialization Interview Revised (FSI-R)  – Parenting Risk module	Masked Coder	x			X	X
Timeline Followback-CM Risk	Father and Mother		х			
Conflict Tactics Scale-Parent Child	Father and Mother	x			x	X
Father-Child Free Play coded using Child Interactive Behavior Rating (CIB)+	Masked Coders	X			X	X (12 month only)
Children's Emotions Scale (RCES)	Mother and Father					
Brief Infant Toddler Social Emotional Assessment (BITSEA) Trauma Symptom Checklist for Young Children (TSCYC) or Trauma symptom checklist for children (TSCC) appropriate for child age	Mother and Father Children >7-Self Report	X			X	X
Kiddie Diagnostic Interview Schedule PTSD Module OR Diagnostic Infant and Preschool Assessment (DIPA) modified PTSD module	Mother and Father	X			x	x
Satisfaction Outcomes						
Client Satisfaction Questionnaire 8 (58)	Father				Х	
Intervention Targets (Mechanisms)						
Unified Protocol Skill Use Scale (UPSUS)122 and select items from the 28-item Brief COPE	Father		X			
Difficulties in Emotion Regulation Scale (59) DERS Short Form	Father	X	Х		x	Х
Reflective Functioning Questionnaire-8 (RFQ)(60)	Father	X	Х			
Parent Reflective Function Questionnaire (PRFQ) (61)	Father	X	X			
Intervention Process Variables						
Working Alliance Inventory (62)	Father and Clinician			Х		
CHANGE Coding	Trained Reliable Coders			Х		
Motivation to Change	Father			Х		

	1			1	1
Therapist Session Report Form	Clinician		x		
Other variables to classify the sample					
STRESS Trauma History and PTSD Scale	Father	Х			
Alcohol Use Disorders identification Test (AUDIT) – Self report(66)	Father	Х			
Drug Abuse Screening Test- 10 (DAST- 10)(67)	Father	Х			

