# Treatment Phase.

Each treatment will be delivered weekly over 18 weeks. Male participants will meet online or be contacted via phone weekly with the RA to complete self-report assessments of IPV behaviors, father-child interactions and *substance use*. The RAs will be blind to the participants' treatment conditions. Study therapists will complete weekly session reports of session content and skill acquisitions based on completed homework.

*Fathers for Change*: F4C focuses on: 1) the fathering role to facilitate engagement, 2) RF to understand self, partner and children and emotion regulation skills to reduce IPV and child maltreatment F4C focuses on understanding of emotional experiences, how they impact thinking and behaviors related to partners, co-parents and children. F4C clients will meet individually with their F4C therapist for 50 minutes per week over 18 weeks.

**Batterer Intervention Program:** The BIP is a psychoeducational intervention that will be delivered in 50- minute individual sessions over 18 weeks. The intervention focuses on the impact of violence on victims, power and control tactics, and societal influences supporting men's violence toward women. The intervention includes didactics and experiential exercises including role plays to teach management skills. anger BIP is typically delivered in a group format, however will also be adapted to an individual Therapies will be delivered either in person or via format as part of the current study. secure/password protected zoom virtual sessions. All Yale safety protocols with regard to COVID-19 will be followed.

**Therapist Training.** Master's level clinicians will be trained to deliver the study interventions. [name] will utilize the therapist training manual, slides and videos generated from her pilot studies to train F4C therapists. She will meet weekly with F4C therapists for supervision. BIP-I and BIP-G therapists will be trained by [name] using the BIP manual and training materials modified for individual treatment delivery. BIP clinicians will meet weekly with [name] for supervision and intervention adherence.

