**Treatment Fidelity.** Each intervention session will be video recorded. Trained coders will rate 20% of sessions for fidelity and change in emotion regulation/reflective functioning during therapy sessions using the F4C/BIP Fidelity Measure and the CHANGE coding system. Tape raters for fidelity will be trained by the PI coding a set of 6 practice tapes. Fidelity feedback will be provided by Drs. [name] (F4C) and [name] (BIP) in their respective supervision sessions with study therapists to ensure fidelity and allow corrective feedback. Tape raters will be trained by [name] for the CHANGE session coding system and will be supervised by [name] at the University of Delaware and [name] at the University of Connecticut. The Change and Growth Experiences Scale (CHANGE; Hayes, Feldman, & Goldfried, 2007) is an observational coding system that assesses processes of change during psychotherapy, including factors that facilitate and inhibit therapeutic change. The CHANGE has been used to code audio and video recordings of sessions or narratives from clinical trials of trauma-focused cognitive behavioral therapy (TF-CBT) for youth (Alpert et al., 2021; Canale et al., 2021; Ready et al., 2015; Yasinski et al., 2016), prolonged exposure, written exposure therapy (WET), and cognitive processing therapy (CPT) for adult PTSD (Alpert, 2021; Alpert et al., 2020; Sloan et al., 2021), as well as cognitive-behavioral treatments for depression (Abel et al., 2016; Adler et al., 2013; Hayes, Feldman, Beevers et al., 2007; Yasinski et al., 2020) and personality disorders (Hayes & Yasinski, 2015). The CHANGE has been used to identify key predictors of treatment dropout and outcomes in each of these clinical trials.

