# Phase II Hypotheses:

**AIM 1 Hypotheses:** Children of fathers who receive F4C (n=180), relative to BIP (n=180), will: (1a) experience less family violence (FV), (1b) have more positive father-child interactions, and (1c) have lower FV-related mental health symptoms (PTSD, internalizing/externalizing) at post treatment and 6- and 12-month follow-ups. The effects of both treatments on father and coparent mental health outcomes will also be examined (1d exploratory). Hypotheses will be evaluated with the broad family of latent (growth) curve models (LGM), which estimate and compare trajectories of change for each case in the data. Group differences in changes will be tested in multiple group LGM models. Following analyses for our primary study hypotheses, we will examine whether child sex moderates child mental health outcomes between the F4C and BIP groups. Power. The planned sample size of 140 F4C and 140 BIP cases provides power of .91 to detect a small to moderate effect size (d = 0.12). The current study with 140 per group (even 126) per group assuming a conservative 30% attrition at follow-up) has sufficient power to determine small differences in changes between intervention groups on outcomes. LGM models for changes in latent rather than observed scores, for three or more waves of data, have the advantage of partialing out measurement error, and increasing the statistical power by at least 20%. See Statistical Design and Power Section for estimation method.

AIM 2 Hypotheses. Compared to BIP, more F4C fathers will show profiles of healthy change in therapeutic targets: (2a) masked coding of in-session RF/ ER (i.e., increased RF and adaptive ER, decreased maladaptive ER), and (2b) between-session self-reported RF/ ER (i.e., increased

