# SECTION VI: PROTECTION OF RESEARCH PARTICIPANTS

1. Confidentiality & Security of Data: Describe the steps that will be taken to secure the data during storage, use and transmission as outlined in the below sections. NOTE: Data can include paper files, data on the internet or websites, computer files, audio/video files, photographs, etc. and should be considered in the responses to the below sections.

Confidentiality with regard to completed research forms will be maintained via a numbered reference system maintained by the PI and Project Directors. Participants' names will appear only on the consent form, HIPPA authorization form, and "key" form in a password protected file only assessable by the PI. All data will be identified by participant ID only. All measures, video and recordings will be labeled by participant ID only. Subjects who decline participation in the study or those who wish to withdraw from the study can continue in their treatment at the outpatient facilities as they would if they were not approached to participate in a study. As stated above to further protect against potential risks to confidentiality for this population, a Certificate of Confidentiality will be obtained. Participants will clearly be informed of the limits of this confidentiality, which are in cases of suspected child abuse or neglect, and imminent risk for harm to self or others (particularly intimate partner or child).

Therapy sessions will be video recorded to ensure that the therapists administer the study treatments within manual guidelines and are engaging the intervention targets of emotion regulation and reflective functioning. To assure the confidentiality and protection of participants with respect to video and audio recording, the following steps will be taken:

- Participants have the right to refuse recording. Participants who consent to recording will be informed that they have the right to stop at any time during any session.
- Each therapist will conduct the recording him/herself. All recording will take place in the treatment facility in private offices.
- During treatment sessions the therapist's behavior is of primary interest for process assessment, the camera will be directed at the therapist.

- Each digital recording will be labeled with the participant's study identification number and a coded session date.

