- The therapist or RA will then store the digital recording on a password protected server. Yale utilizes a HIPAA compliant, encrypted and fire wall protected server called One Drive. Once the files are uploaded onto the One Drive server, the session will be deleted from the video camera data cards.
- Access to the recordings will be limited to specially trained research raters who will rate the tapes according to established process rating systems. All ratings will be done in esearch offices at Yale, UCONN or U of Delaware.
- Upon completion of these ratings, the recordings will be deleted.

Aside from video recordings of sessions, all other study data will be de-identified and stored within the REDCap database. Consent forms and releases of information for the study will be kept in a secure file on a password protected computer.

The treatments provided could be an option for mandated treatment. If clients wish their study therapist to provide information to court support services or some other entity related to their participation in treatment, the study therapist and/or PI will do so with a signed release from the client. A form letter will be created that indicates the dates of program attendance, nature of the treatment being provided and completion of treatment. No information about the research data collected or study components will be provided only their attendance and successful or unsuccessful completion of treatment. If a client wishes for other information to be disclosed, they can indicate this on the release form.

Criminal and child protection records will be collected by providing an excel sheet with participant names and dates of birth to the Court Support Services Division of the State of CT and the Department of Children and Families along with signed releases of information from participants to provide their names to the agency to provide data to us. We will provide no other information to DCF or CSSD about the participants. Data will be entered into the excel sheets by CSSD or DCF staff and returned to the project director. These will be transferred from the agency to the project director using secure data transfer (OneDrive).

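### Hypothesis 2a relies on masked coding of therapy sessions, but masking to treatment arm is neither described nor plausible

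*Combined protocol and SAP*

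**What the plan says.** Aim 2 compares change in reflective functioning (RF) and emotion regulation (ER) between Fathers for Change (F4C) and the Batterer Intervention Program (BIP). The observer-rated part is given in Section IV, Phase II Hypotheses, as "2a) masked coding of in-session RF/ ER (i.e., increased RF and adaptive ER, decreased maladaptive ER", and the same claim appears under Aims for Phase II. Hypothesis 2b uses fathers' own reports between sessions.

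On who codes, the Treatment Fidelity paragraph says: "Trained coders will rate 20% of sessions for fidelity and change in emotion regulation/reflective functioning during therapy sessions using the F4C/BIP Fidelity Measure". The sentence goes on to name the CHANGE system. The paragraph then treats training separately. For fidelity, "Tape raters for fidelity will be trained by the PI coding a set of 6 practice tapes"; CHANGE raters have their own training and are supervised from two other universities. The Phase I aims describe the purpose of the fidelity instrument: "Develop a fidelity measure to distinguish F4C from BIP for therapist fidelity coding".

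On what is recorded, Section VI item 1 says that "the camera will be directed at the therapist". Table 1 gives the rater for CHANGE as "Trained Reliable Coders", whereas the rows for the Family Socialization Interview (FSI-R) and the father-child play task say that the coders are masked.

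On research assistants (RAs), the Treatment Phase text says "The RAs will be blind to the" participants' allocated condition. Section VI item 1 says: "The therapist or RA will then store the digital recording on a password protected server".

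**The concern.** Fathers know which treatment they receive, so self-report cannot be protected from expectation. The in-session codes are the only observer-rated evidence on the proposed mechanism during treatment, and the word masked is what gives them added weight. If coders can tell the arm, their ratings are open to expectancy on the very constructs that F4C is designed to change. Any resulting bias would enter the Aim 2 trajectory classes and pass into Aim 3, where class membership is the mediator. A report that repeated the word masked without qualification would claim a protection that the design does not plausibly provide.

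A smaller and separate matter is that staff who are meant to be blind, and who collect the weekly violence logs and the follow-up assessments, are allowed to handle session recordings.

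**Working it through.** The plan gives no figure for this point, so there is none to reproduce. The check sets the sections side by side and then counts the sessions concerned.

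1. **Masked to what?** Aims for Phase II and Phase II Hypotheses both use the word without an object. Arm, session number, outcome and study hypotheses are all possible readings.

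2. **What does the coder see?** The material is video of the therapy. According to the Treatment Phase text, F4C works on fatherhood, RF and ER, while BIP teaches about harm to victims, coercive control and social attitudes to violence. The camera faces the therapist, and therapists are described, trained and supervised by arm. Either the content or a recognised therapist would usually identify the treatment.

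3. **Is concealment described?** No section mentions transcripts stripped of arm cues, shuffled session order or a separation of rating tasks. The file label (study number and coded session date, Section VI item 1) does not show the arm, but the recording itself does.

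4. **Does Table 1 support the claim?** It uses the term masked for the FSI-R and play coders and not for CHANGE. This silence is not a contradiction, but the schedule does not back the wording of 2a.

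5. **Are the fidelity and CHANGE raters the same people?** One sentence covers both tasks; the training statements differ. Section VI item 6 describes overseers of coders who rate RF and ER content and does not mention fidelity. The question is unsettled. If the same people do both, completing an instrument built to separate the arms would itself reveal the arm. If they do not, steps 2 and 3 still apply.

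6. **Where do the codes go?** Under Aim 2, in-session and between-session targets are first modelled separately, then in combinations of six targets. The resulting grouping is the Aim 3 mediator. The codes therefore contribute to the classes alongside self-report and do not alone define them.

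7. **How many sessions?** Inputs: 20% coded (Treatment Fidelity), 18 sessions (Treatment Phase), 280 fathers (Participant Population).
   - Per father: 0.20 × 18 = 3.6.
   - In total: 3.6 × 280 = 1,008.
   - This is a ceiling. It assumes full attendance and that nobody uses the right to refuse recording.

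8. **How large could a bias be?** The documents give no estimate. For scale only, assume no true difference, a coder shift of b standard deviations towards F4C, and a two-sided 5% two-sample normal test with 140 per arm.
   - Standard error: √(2/140) = 0.1195.
   - Rejection rate: 1 − Φ(1.96 − b/0.1195) + Φ(−1.96 − b/0.1195).
   - Results: about 13% for b = 0.1, 39% for b = 0.2 and 71% for b = 0.3.

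   The values of b are assumptions, and this is not the planned trajectory model. A shift that is constant over sessions would move the level of a trajectory; a shift that grows as the coder expects improvement would move its slope, which is what 2a is about. Masking to session number is therefore worth having even where the arm is visible.

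9. **RA handling.** RAs are to be blind, may store recordings, and have access to the file linking study numbers to participants (Section VI item 4; item 1 of the same section restricts the key to the principal investigator). Against this, the therapist makes the recording, and item 1 limits access to recordings to trained raters.

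**The case against.** The strongest reply is that masked may never have meant masked to arm. Trials of talking treatments often mask raters to outcome or session order only, and such masking would fit the words of 2a. This stands: one cannot say that a promised masking has failed, only that it is undefined and that the arm-masked reading is not credible.

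A reader might infer from the single sentence in Treatment Fidelity that CHANGE coders also score fidelity and so must know the arm. The separate training and supervision statements do not support that as fact, and on balance they point towards separate pools.

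A reader might also infer that RA blinding is lost. The documents do not show this. No section says that the storing RA views a recording, or is the person who collects that father's outcomes. The FSI-R, which the plan calls its primary outcome measure, is rated by a masked coder, although reports gathered by RAs inform that rating. Nor does RA storage bear on hypothesis 2a.

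Finally, an expectancy effect favouring F4C is assumed rather than demonstrated, hypothesis 2b is untouched by it, and the rejection rates above rest on assumed shifts. All of this is fair and limits the point to what the masking claim can bear.

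**Conclusion.** The point holds in limited form. As written, 2a invites the reading that coders do not know the treatment, and nothing in the design makes that plausible. This rests on two inferences: that the content differs enough to be recognised on video, which the treatment descriptions support, and that therapists do not cross arms, which the supervision arrangements suggest but do not state. The first is sufficient alone.

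Up to 1,008 coded sessions, 3.6 per father, are concerned. The size and direction of any bias in the classes or the mediated effect cannot be computed from the documents, and the illustrative rates should not be quoted as estimates. RA storage of recordings is an avoidable route to unmasking, no more than that.

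**What to change.** - In Aims for Phase II and Phase II Hypotheses, state that 2a is coded by raters who are not masked to treatment but are masked to participant outcome and, as far as session content allows, to session number.
- In Treatment Fidelity, specify that sessions are presented to CHANGE coders in random order, that the coded date on the file does not let them reconstruct the sequence, and that no rater scores both fidelity and CHANGE for the same father.
- Make the CHANGE row of Table 1 say the same.
- In Section VI item 1, remove the RA from the sentence on storing recordings, so that therapists upload them.

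The cost is wording and the assignment of existing raters, with no added staff. The masking claim becomes weaker and rater assignment slightly more constrained. Masking to session number will be incomplete where a session's topic shows its place in the manual, hence the qualified wording.
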